8.4.2 Safety concerns

The PROSPECT trial involves surgical operations for prolapse which are well established in clinical practice, and others which have been developed in response to the poor success rates for standard primary surgery (30% of women will require a further operation). New operations involve the use of mesh. Their effectiveness is largely unproven and adverse effects may include pain, haemorrhage, infection, dyspareunia and mesh erosion, as well as damage to pelvic organs. However, these adverse effects may also occur after 'standard' prolapse surgery. The relevant guidelines for reporting serious adverse events will be followed.

Possible expected occurrences

In this study the following occurrences are potentially expected:

- Possible (expected) intraoperative occurrences associated with surgery are: injury to organs or blood vessels, excess blood loss, blood transfusion, anaesthetic complications, death.
- Possible (expected) occurrences following surgery are: thrombosis, infection (UTI, sepsis, abscess), pain, urinary retention, bowel obstruction, constipation, mesh erosion, excess blood loss, haematoma, vaginal adhesions, skin tags, granulation tissue, new or persistent urinary tract symptoms, death.

Details of any of the occurrences listed above will be recorded on the case report forms (CRFs) and reported to the DMC.

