8.4.3 Procedure for reporting untoward and related SAEs in this study

A Serious Adverse Event (SAE) in PROSPECT is defined as an event occurring to a research participant that is both:

- related (resulted from administration of any of the research procedures) and
- unexpected (ie the type of event that is not listed above as an expected serious occurrence) that causes death, is life threatening, requires hospitalisation or prolongation of an existing hospital admission, or results in significant incapacity/disability.

All SAEs will be recorded on the Serious Adverse Event Report form. In addition, SAE forms will record all deaths for any cause during the course of the study.

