8.4.4 Reporting responsibilities of the CI

The CI will be automatically notified of any potential related and unexpected SAEs. If, in the opinion of the local PI and the CI, the event is confirmed as being related and unexpected, the CI will submit a report to the main REC, the study sponsor and the DMC within 15 days of the CI becoming aware of it.

Collaborators and participants may contact the chairman of the TSC through the Study Office about any concerns they may have about the study. If concerns arise about procedures, participants or clinical or research staff (including risks to staff) these will be relayed to the Chairman of the DMC.

As the trial arm to which women are allocated cannot be blind to the gynaecologist or theatre staff after randomisation has occurred, unblinding is not an issue in this trial. A record of the operative procedures actually carried out will be available in the medical notes if required clinically.

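### Death is on the protocol's list of expected occurrences, so on the plain wording a procedure-related death does not trigger the 15-day report to the ethics committee, sponsor and DMC

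*Protocol*

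**What the plan says.** The rule is spread over three consecutive sections of the protocol.

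- **8.4.2 Safety concerns** gives two lists of expected occurrences. The intraoperative list ends "excess blood loss, blood transfusion, anaesthetic complications, death" and the postoperative list ends "granulation tissue, new or persistent urinary tract symptoms, death". On handling, it says: "Details of any of the occurrences listed above will be recorded on the case report forms (CRFs) and reported to the DMC". It also makes a general commitment: "The relevant guidelines for reporting serious adverse events will be followed".
- **8.4.3 Procedure for reporting untoward and related SAEs** sets two conditions that must both hold. The event must be "related (resulted from administration of any of the research procedures) and" it must also be "unexpected (ie the type of event that is not listed above as an expected serious occurrence) that causes death", or meet one of the other seriousness criteria that follow. The section adds that "SAE forms will record all deaths for any cause during the course of the study".
- **8.4.4 Reporting responsibilities of the CI** sets the expedited route. If the local PI and the CI consider the event "confirmed as being related and unexpected, the CI will submit a report to the main REC", and also to the sponsor and the DMC, within 15 days of becoming aware of it.

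Section 8.3.3 Sponsorship adds a general duty on the CI, exercised through the TSC, to have suitable systems for expedited and routine reporting of adverse effects. The SAP does not deal with safety reporting.

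**The concern.** Death is an outcome that makes an event serious. Section 8.4.3 uses it that way, as the first of its seriousness criteria. Section 8.4.2 also treats death as a type of event and places it on the list that exempts events from being unexpected. The same word therefore makes an event serious in one section and exempts it in another.

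What is at stake is the timing and reach of oversight for the gravest harm the surgery could cause. A related, unlisted, non-fatal event leading to readmission must reach the ethics committee, sponsor and DMC in 15 days. A related death need not. The listed occurrences include injury to organs or blood vessels, which is the hazard that Appendix I, section 1.3, associates with blind trocar insertion of mesh kits.

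**Working it through.** No calculation applies. The check is to follow a case through 8.4.2, 8.4.3 and 8.4.4 and see whether the 15-day report is required.

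**Two readings of unexpected in 8.4.3.** Under reading 1 (plain wording), an event of any type on the 8.4.2 list is expected, and death is on the list. Under reading 2 (narrower), expectedness is judged by the causal event, and death is only its consequence.

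| Case, all judged related | Reading 1 | Reading 2 |
|---|---|---|
| Death from a listed complication | Listed, no 15-day report | Cause listed, no 15-day report |
| Death from an unlisted type of event | Death listed, no 15-day report | Cause unlisted, 15-day report |
| Non-fatal, unlisted event requiring hospitalisation | 15-day report | 15-day report |

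The two readings differ only in the second row. That row is narrow, because the listed causes already cover organ or vessel injury, blood loss, anaesthetic complications, thrombosis, sepsis and bowel obstruction. The lists carry no severity grading, so a fatal instance of a listed type is as expected as a mild one.

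**Do other provisions fill the gap for a related death?**

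| Provision | What it does | Deadline | Ethics committee or sponsor named as recipient |
|---|---|---|---|
| 8.4.2, listed occurrences | CRF record and report to DMC | None | No |
| 8.4.2, relevant guidelines | General commitment, guidelines not named | None | No |
| 8.4.3, all deaths | Record on SAE form | None | No |
| 8.3.3, CI duty | General commitment to expedited and routine reports | None | No |

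**Would deleting death from the lists be enough?** After deletion, both readings give the same result. A death from an unlisted type of event is reported in 15 days. A death from sepsis, haemorrhage or organ injury is still of a listed type, and so is still not reported under 8.4.4. The first row of the first table does not change. Only a rule in 8.4.4 that does not depend on the list changes it.

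**The case against.** The strongest reply is that the protocol does not neglect deaths. Every death from any cause goes on an SAE form. Listed occurrences go to the DMC, which advises the TSC, and the TSC can modify intake (8.4.1). Section 8.4.4 lets concerns be relayed to the DMC chair. Sections 8.3.3 and 8.4.2 commit to expedited reporting and to guidelines in general terms. The wording of 8.4.3 can also bear reading 2. All of this stands, and it limits the point to the absence of a stated deadline and of a stated route to the ethics committee and sponsor.

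Three stronger inferences are tempting, and the documents do not support them.

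- A reader might infer that the ethics committee and sponsor would receive no report at all. The general commitments in 8.3.3 and 8.4.2 rule out that certainty. What can be said is that no specific route is written down.
- A reader might take the DMC meetings listed by months 12, 24, 36 and 48 (7.3 and 7.4) and infer a delay of up to 12 months, or about 6 on average. Section 8.4.2 does not tie DMC reporting to meetings, and 8.4.1 leaves room for further meetings. Nor would 12 months be a maximum: 7.4 lists no DMC meeting after month 48 while follow-up runs to month 66, a span of 66 − 48 = 18 months. The supportable statement is that no deadline is given.
- A reader might cite 3.1 as bringing in the mesh kit despite scarce safety data. That section gives the scarcity as the reason for restricting the kit to secondary repairs, which is a safeguard.

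It is also fair to say that the point does not touch the estimand or the analysis. Appendix IV shows recruitment had closed by August 2013, so an amendment to this version could affect few operative deaths.

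**Conclusion.** The inconsistency is real. On the plain wording, no procedure-related death triggers the 15-day report. On the narrower reading, a death from an unlisted type of event does, but one from a listed complication still does not. On either reading, the deaths most plausibly caused by this surgery fall outside the expedited route, and no other provision states a deadline or an ethics committee or sponsor recipient for them.

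The size is a gap in a rule, with no measured delay or count behind it. Two assumptions are needed. The unnamed guidelines do not themselves impose a timed route, which cannot be checked from the documents. Procedure-related deaths are few, since no operative mortality rate is given. The finding concerns how quickly and to whom such deaths are reported; it does not imply that they go unrecorded.

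**What to change.** Reconcile 8.4.2, 8.4.3 and 8.4.4 with two linked changes.

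1. Add to 8.4.4 that any death judged related to the research procedures, under the existing assessment by the local PI and the CI, is reported to the main ethics committee, sponsor and DMC within the existing 15 days, whether or not its cause is on the expected list. This sentence closes the gap.
2. Remove death from both lists in 8.4.2, so that it serves only as a seriousness criterion. This is for consistency and is not sufficient alone.

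Keep the recording of all deaths on SAE forms. The relatedness assessment, deadline and recipients are unchanged. The cost is one protocol amendment and, on the assumption above, a small number of extra expedited reports.

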8.4.3 Procedure for reporting untoward and related SAEs in this study

A Serious Adverse Event (SAE) in PROSPECT is defined as an event occurring to a research participant that is both:

- related (resulted from administration of any of the research procedures) and
- unexpected (ie the type of event that is not listed above as an expected serious occurrence) that causes death, is life threatening, requires hospitalisation or prolongation of an existing hospital admission, or results in significant incapacity/disability.

All SAEs will be recorded on the Serious Adverse Event Report form. In addition, SAE forms will record all deaths for any cause during the course of the study.

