Because of the importance of mesh in (theoretically) reducing the repeat surgery rate, we further propose that an additional primary clinical outcome will be the rate of repeat surgery for prolapse (any compartment). For repeat prolapse surgery within 14 years, if the event rate for the standard midline repair is assumed to be 25%, the power to detect a 10% absolute difference in reoperation rates compared with either biological or synthetic mesh would be 90% if the current response rate was maintained and 66% if the response rate falls to 50%.

The primary economic outcome measure of cost effectiveness will remain the same: the incremental cost per QALY (QALYs based on the EQ-5D⁶). In addition, because of all the potential problems associated with the use of mesh in prolapse surgery, serious adverse events will be included as a secondary outcome.

Following completion of the 14 year dataset, the full trial data will be reported for the randomised and the corresponding comprehensive cohort according to the trial

Statistical Analysis Plan. Analyses related to the two randomised trials (primary and secondary surgery) will be undertaken on an intention-to-treat basis allowing for repeated (two-yearly) symptom and quality of life measurements. Data from Cohort women will be analysed according to treatment received (mesh or no mesh surgery), separately according to primary or secondary procedure, or upper vaginal prolapse surgery only.

[figure not shown]
Management

Trial management, data collection and analysis will be undertaken in the PROSPECT Trial Office, HSRU, University of Aberdeen, under the supervised of the PROSPECT Project Management Group. This group consists of the grant holders and representatives from the Study Office.

References

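### The only SAE definition excludes expected event types, so the long-term SAE outcome, added because of mesh problems, would not count a mesh erosion even if it led to readmission

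*Protocol*

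**What the plan says.** Protocol section 8.4.3 opens: "A Serious Adverse Event (SAE) in PROSPECT is defined as an event occurring to a research participant that is both". Two conditions follow. The first is "related (resulted from administration of any of the research procedures) and", which leads into the second, "unexpected (ie the type of event that is not listed above as an expected serious occurrence". The usual seriousness criteria (death, threat to life, admission or longer stay, significant incapacity) apply on top of these. Deaths from any cause also go on SAE forms.

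The only list to which the second condition can refer is in section 8.4.2. For surgery itself it reads: "Possible (expected) intraoperative occurrences associated with surgery are: injury to organs or blood vessels, excess blood loss". For the period afterwards: "Possible (expected) occurrences following surgery are: thrombosis, infection (UTI, sepsis, abscess), pain, urinary retention, bowel obstruction, constipation, mesh erosion". Neither part carries a severity limit. The same section introduces the mesh operations by saying that their "adverse effects may include pain, haemorrhage, infection, dyspareunia and mesh erosion, as well as damage to pelvic organs".

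Appendix IV, on long-term follow-up, then states that "because of all the potential problems associated with the use of mesh in prolapse surgery, serious adverse events will be included as a secondary outcome". It does not define the term. It refers the long-term analysis to the trial SAP, but the SAP does not mention serious adverse events and its last planned analysis is at 24 months.

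**The concern.** A rule that combines relatedness with unexpectedness selects events for expedited reporting. Its purpose is to catch the unforeseen. An outcome meant to compare harm between arms has the opposite purpose: it must count serious events whether or not they were foreseen. Here the first kind of rule is the only definition available to an outcome of the second kind.

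What is at stake is how the long-term result reads. A table of serious adverse events by arm, introduced as a response to mesh problems, would be taken as a count of serious mesh harm. Under 8.4.3 most recognised mesh harms could not enter it. For erosion of a prolapse mesh the gap is one-sided, because it can arise only where such a mesh was placed.

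**Working it through.** The check is mainly textual, and the plan states no figure to reproduce.

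**Step 1. Is there another definition?** Section 8.4.3 states its definition for the study as a whole. Neither Appendix IV nor the SAP offers a different one. Section 8.4.4 speaks of SAEs that are related and unexpected, a qualifier that would be redundant if every SAE already met both conditions. This suggests that a reporting rule was written down as the general definition.

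**Step 2. Apply the definition to the harms that 8.4.2 names for the mesh operations.**

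| Harm | Entry on the expected list | Can it be unexpected? |
|---|---|---|
| Pain | after surgery | no |
| Haemorrhage | excess blood loss, during and after surgery | no |
| Infection | after surgery | no |
| Mesh erosion | after surgery | no |
| Damage to pelvic organs | injury to organs, during surgery only | no, if judged by type of event; arguable if late |
| Dyspareunia | none | yes |

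Five of the six are on the list, reading haemorrhage as excess blood loss and organ damage as organ injury. An erosion leading to admission and surgery meets a seriousness criterion but fails on unexpectedness, so it is not an SAE.

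**Step 3. Direction.** Leaving out erosion of a prolapse mesh removes events only from women who received mesh, and so mainly from the mesh arms. For infection, pain, blood loss and organ injury, 8.4.2 itself says that they can follow standard repair too. The documents give no basis for a direction there.

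**Step 4. Size.** Inputs:
- Women randomised in the primary trial (SAP Table 2): biological 255 + 114 = 369; synthetic 256 + 181 = 437.
- Erosion rates (Appendix I, section 1.2.2): 6% for absorbable biological mesh and 10% for non-absorbable synthetic mesh.

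Erosions of any severity = rate × women:
- Biological: 0.06 × 369 = 22.1, about 22.
- Synthetic: 0.10 × 437 = 43.7, about 44.

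If a fraction *s* of these were serious, the SAE outcome would omit about 22*s* and 44*s* women. The documents do not give *s*. Over its full range from 0 to 1, the omission runs from 0 to 22 and from 0 to 44. These ends hold only if the anterior-repair review rates apply to all repairs in the trial and every woman received her allocated mesh. They do not bound the 14-year figure, because that section reports no long-term data.

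**The case against.** The strongest reply is that nothing is lost except a label. Expected occurrences go on case report forms and to the DMC (8.4.2). Post-operative morbidity and mesh erosion or removal are main-trial secondary outcomes (protocol 6.2, SAP Secondary Outcomes), with treatment effects and intervals planned for all outcomes. Appendix IV collects postoperative complications and the treatment they needed, checks readmissions against HES and ISD, and adds repeat prolapse surgery as a primary outcome. All of this stands. A reader might infer that serious mesh harm goes unrecorded; the documents do not support that. The point is confined to the outcome called serious adverse events.

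A second reply is that Appendix IV does not cite 8.4.3, and that a reading which removes mesh problems defeats the outcome's stated reason. That shows what was probably intended. It does not supply a definition, and an analyst who follows the only written one would obtain the narrow count.

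Three further inferences are tempting and should not be drawn:
- That the main-trial results are affected. Serious adverse events are not a listed outcome in protocol 6.2 or in the SAP.
- That unblinded local investigators would bias the long-term count through their judgement of relatedness. Section 8.4.4 describes that judgement for 15-day reporting. Appendix IV describes no such step for questionnaire, HES/ISD or case-record data.
- That 22 and 44 women are missed serious events. They are erosions of any severity, at rates from a review section on anterior prolapse that draws partly on non-randomised studies.

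One practical objection also stands. The long-term sources do not list threat to life or incapacity as collected items, and counting every admission over 14 years could dilute a mesh effect with unrelated events. The fix has to allow for both.

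**Conclusion.** The concern holds in a limited form. Under the only definition in the documents, the Appendix IV outcome leaves out most of the harms that prompted it, mesh erosion among them. This is an unsuitable rule, not just a missing detail. The conclusion rests on carrying the study-wide definition into Appendix IV, which is the natural reading because no alternative is given. Late organ injury is arguable, deaths are on SAE forms regardless, and dyspareunia could still qualify if related and serious.

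The one-sided omission is established for erosion of a prolapse mesh only. Its size cannot be computed without a serious fraction. The correction is worth making because the result could be misread and the change is cheap, but the underlying data are not at risk.

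**What to change.** Reconcile protocol sections 8.4.2, 8.4.3 and 8.4.4 with Appendix IV:

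1. Keep the related-and-unexpected rule in 8.4.3 for expedited reporting only, and name it as such.
2. In Appendix IV, define the serious adverse event outcome by seriousness regardless of expectedness, limited to what questionnaires, HES/ISD and case-record verification can identify: death, hospital admission and reoperation.
3. Report it by allocated arm, with prolapse- or mesh-related events on a separate line from all-cause events, so that unrelated admissions do not hide a mesh effect.
4. Add the definition and the comparison to the SAP, or to a long-term addendum, since the present SAP ends at 24 months.

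The cost is revised wording and some work to classify events from sources already planned, with no added visits. Reported counts will be higher and will include events unrelated to the surgery, which is why the separate line is needed.

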8.4.4 Reporting responsibilities of the CI

The CI will be automatically notified of any potential related and unexpected SAEs. If, in the opinion of the local PI and the CI, the event is confirmed as being related and unexpected, the CI will submit a report to the main REC, the study sponsor and the DMC within 15 days of the CI becoming aware of it.

Collaborators and participants may contact the chairman of the TSC through the Study Office about any concerns they may have about the study. If concerns arise about procedures, participants or clinical or research staff (including risks to staff) these will be relayed to the Chairman of the DMC.

As the trial arm to which women are allocated cannot be blind to the gynaecologist or theatre staff after randomisation has occurred, unblinding is not an issue in this trial. A record of the operative procedures actually carried out will be available in the medical notes if required clinically.

8.5 Ethical issues and arrangements

The North of Scotland Ethics Committee (NOSRES) has reviewed this study. The study will be conducted according to the principles of good practice provided by Research Governance Guidelines.

We believe this study does not pose any specific risks to individual participants beyond those of any surgery, nor does it raise any extraordinary ethical issues. It is possible that cultural or religious factors may affect the choice of graft material, as some biological grafts are of porcine origin (which may be inappropriate for certain religious groups). This will be taken into account in choosing appropriate materials for particular groups.

8.5.1 Risks and benefits

The benefit to the women participating in the trial is the chance of receiving the optimum treatment for their prolapse, although we do not know what that treatment is. The risks are that they may have a sub-optimal operation but any operation carries a risk, and it is not known which is optimal or more risky. The benefit to society is that, at the end of the trial, it will be known which operations are most effective and cost-effective. Extra information will be available on safety and efficacy outcomes through analysis of data from the non-randomised women included in the Comprehensive Cohort.

